7.2 Study completion and post-study treatment

Each subject is required to complete the study in its entirety. No further study treatment will be made available to a subject after they have completed the study in its entirety.

Study completion is defined as:

- When the last subject completes the EOS visit
- and
- Any repeat assessments or follow-up associated with the EOS are documented appropriately by the Investigator
- or
- [The date of an early study termination decision](#)

Novartis

Confidential

Page 57

Amended Protocol Version No. 01 (Clean)

Protocol No. CCLG561X2201A

At a minimum, subjects must be contacted for safety evaluations during the 28 days following the follow up visit. Documentation of attempts to contact the subject must be recorded in the source documentation.

The Investigator must provide follow-up medical care for all subjects who are prematurely withdrawn from the study, or must refer them for appropriate ongoing care. This care may include:

- Enrollment in an extension study
- Standard of care treatment as determined by the nature of their condition

The following are recommendations for initiating other treatment outside the study:

- Referral to another medical professional suitable to provide follow-up medical care
- Inform current medical provider on subject's current medical status

7.2.1 Lost to follow-up

For subjects whose status is unclear because they fail to appear for study visits without stating an intention to discontinue or withdraw, the Investigator should show "due diligence" by documenting in the source documents steps taken to contact the subject (e.g. dates of telephone calls, registered letters, etc.). A subject is not formally considered lost to follow-up until his/her scheduled end of study visit would have occurred.

7.3 Withdrawal of consent

Subjects may voluntarily withdraw consent to participate in the study for any reason at any time.

Subject withdrawal of consent includes the following conditions:

- Does not want to participate in the study
- Does not want any further visits or assessments
- Does not want any further study related contact
- Does not allow analysis of already obtained biologic material

If a subject withdraws consent, the Investigator must make every effort to determine the primary reason for this decision and record this information. Study treatment must be discontinued and no further assessments conducted. All biological material that has not been analyzed at the time of withdrawal must not be used. Further attempts to contact the subject are not allowed unless safety findings require communicating or follow-up.

7.4 Study stopping rules

Under any of the following conditions, the current study/arm(s) are placed on temporary hold and potentially halted, pending full review of the clinical data by the Investigator and Sponsor:

- Two or more incidents of the same SAE that, in the opinion of the Investigator, are related to the study drug(s) and not the injection procedure
- The principal Investigator (or his/her designee) and the sponsor consider that the number and/or severity of AEs justify discontinuation of the study
- The Sponsor requests it

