3.2 Rationale of study design

The design of this study will address the primary objectives of efficacy and safety of every 4 weeks IVT injection of monotherapy with CLG561 (10 mg), as well as the combination of LFG316 and CLG561 (5 mg of each) in subjects with GA. Since there is currently no product approved for the treatment of GA, no active comparator is included in the current study. The control for this study will be a sham injection, which is a common and well-established method of control for studies of IVT medications.

Subjects and certain study personnel, but not the Investigator or Sponsor, will be masked to treatment randomization. This approach was chosen for two reasons:

1. Opalescence of the IVT formulation is likely to be visible in the peripheral vitreous, particularly at early visits and would identify actively treated subjects to the study ophthalmologists
2. The primary endpoint is based on objective evaluations by a central reading facility, which will be masked to treatment assignment

Treatment randomization between the active arms and sham allows the evaluation of safety characters of CLG561 as a monotherapy and in combination with LFG316 in a balanced and objective manner. All study subjects will undergo the same study assessments and receive their assigned study treatments under the same dosing interval (every 28 days). All treatment arms will proceed in parallel to each other.

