3.6 Risks and benefits

The risk to subjects in this trial is minimized by adherence to the eligibility criteria, close clinical and safety monitoring, and study/arm(s) stopping rules.

An estimated total of 288.5 mL of blood is planned to be collected over a period of approximately 451 days, from each subject. Additional samples for monitoring of safety findings may be necessary. Blood sampling is not considered to be a risk for this population.

Intravitreal LFG316 up to 5 mg has been administered to over 190 subjects. Over 2000 injections have been administered up to the 10 mg dose. No drug related AEs were noted. CLG561, as a single IVT injection, has been administered to 31 subjects in escalating doses of up to 10 mg. No drug related AEs were noted. A summary of the known and potential risks and benefits associated with CLG561 and LFG316 can be found in the IB.

All IVT injections carry the risk of endophthalmitis, retinal detachment, vitreous or retinal hemorrhage, cataract, elevated intraocular pressure, and ocular inflammation. All of the above conditions are apparent on eye exam, and most cause symptoms that prompt the subject to seek evaluation.

With respect to endophthalmitis, current best clinical practices are used to reduce the risk of endophthalmitis. Despite these practices, endophthalmitis rates may approximate 1 in 1,000 to 1 in 20,000.

As with any antibody, CLG561 or LFG316 are expected to carry the risk of anaphylaxis or hypersensitivity reactions. CLG561 and LFG316 may also elicit the formation of human ADA.

Novartis

Confidential

Page 48

Amended Protocol Version No. 01 (Clean)

Protocol No. CCLG561X2201A

Risks involved in systemic inhibition of properdin

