- In studies utilizing EDC (electronic data capture), all available information for the SAE must be entered immediately into the EDC system. Note: Should the Electronic Data Capture (EDC) system become non-operational, the site must complete the appropriate paper SAE Form. The completed form is faxed to the study Sponsor at [name] within 24 hours of the Investigator's or site's awareness; however, the reported information must be entered into the EDC system once it becomes operational.
- Sponsor representatives and their contact information are provided in the MOP that accompanies this protocol.
- Additional information for any applicable event is to be reported as soon as it becomes available.

In addition to the reporting of SAEs to the study sponsor, the SAE must be reported to the IRB / IEC according to their requirements.

If the SAE was due to a hospitalization of the subject, a copy of the discharge summary is to be forwarded to the study Sponsor as soon as it becomes available. In addition, a letter from the Investigator that summarizes the events related to the case as well as results of any relevant laboratory tests also may be requested. Further, depending upon the nature of the SAE, the Sponsor may request copies of applicable portions of the subject's medical records.

An assessment of seriousness will also be performed for all AEs by a study Sponsor physician utilizing the same criteria. If an AE reported for an Investigator's subject is upgraded to a SAE by a study Sponsor physician, the Investigator will receive a notification by the study Sponsor.

Adverse Events of Special Interest

An AE of special interest is one of scientific and medical concern specific to the sponsor's product, route of administration or program where ongoing monitoring and rapid communication by the Investigator to the sponsor may be appropriate. These AEs may be serious or non-serious. Applicable AEs may require further investigation in order to characterize and understand, and depending upon the nature of the event, rapid communication by the trial sponsor to other parties may also be required. These AEs of special interest must be reported using the same mechanism (EDC or fax) and timeframe (i.e., within 24 hours of the Investigator's or site's knowledge of the event) as described previously for SAEs.

The AEs of special interest include the following:

- Endophthalmitis
- Grade ≥ 3 aqueous flare and/or Grade 4 aqueous cells (see MOP for grading scale)

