9.4 Intensity and causality assessments

For every AE, the Investigator must assess the intensity (severity) and causality (relationship to study treatment). Specifically, events must be classified as mild, moderate, or severe. The assessment of causality will be based upon the categories of related and not related. These classifications must be based on the following definitions:

Intensity (Severity)

- | | |
|----------|---|
| Mild | An event is mild if the subject is aware of, but can easily tolerate the sign or symptom. |
| Moderate | An event is moderate if the sign or symptom results in discomfort significant enough to cause interference with the subject's usual activities. |
| Severe | An event is severe if the sign or symptom is incapacitating and results in the subject's inability to work or engage in their usual activities. |

Novartis

Confidential

Page 77

Amended Protocol Version No. 01 (Clean)

Protocol No. CCLG561X2201A

Causality

Related AEs classified as related may be either definitely related or possibly related where a direct cause and effect relationship between the study treatment and the event has not been demonstrated but there is a reasonable possibility that the event was caused by the study treatment.

Not Related AEs classified as not related may either be definitely unrelated or simply unlikely to be related (i.e., there are other more likely causes for the AE).

An assessment of causality will also be performed by a study sponsor physician utilizing the same definitions. For a serious AE reported by an Investigator as not related that upon review of the available data by the study sponsor physician is assessed (upgraded) to be related, the Investigator will receive a notification.

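### Read literally, the only numeric hold criterion in section 7.4 does not count an SAE to which both drug and injection may have contributed, such as endophthalmitis

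*Protocol*

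**What the plan says.** Section 7.4 lists three conditions for a temporary hold of the study or an arm.

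- The first sets a threshold of two for any one type of SAE and counts only cases that, "in the opinion of the Investigator, are related to the study drug(s) and not the injection procedure".
- The second applies when the principal investigator and the sponsor "consider that the number and/or severity of AEs justify discontinuation of the study".
- The third is a request by the sponsor.

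Only the first carries a number.

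Section 3.6 states: "All IVT injections carry the risk of endophthalmitis". It adds that, despite best practice, "endophthalmitis rates may approximate 1 in 1,000 to 1 in 20,000". The same section says that CLG561 may in theory predispose to endophthalmitis. It gives local immunosuppression as a theoretical route to the same event where it discusses C5 inhibition.

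On causality, section 9.4 says: "The assessment of causality will be based upon the categories of related and not related". The relationship rated is to study treatment, and a reasonable possibility is enough for related. It also says: "An assessment of causality will also be performed by a study sponsor physician utilizing the same definitions".

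**The concern.** An infection inside the eye after an intravitreal injection can have two causes at once: the needle brings in the organism, and a complement inhibitor may weaken the local defence. An investigator who suspects the drug will seldom be able to rule out the needle. If the criterion requires that the procedure played no part, the automatic trigger can stay silent for an ocular harm that the protocol itself foresees.

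Three features add some weight:

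- The sham is needle-free, so the trial has no concurrent rate of procedure-related endophthalmitis.
- Section 10.3 requires no data monitoring committee, and the committee hold in section 10.5 is tied to drug-related AEs.
- Section 3.6 says that the combination has not been given to humans before.

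**Working it through.** **1. The two readings of the first criterion**

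| Investigator's opinion of the SAE | Literal reading | Contrast reading |
|---|---|---|
| Drug only | counts | counts |
| Procedure only | does not count | does not count |
| Drug and procedure both possible | does not count | could count |

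The readings differ only in the last row. Section 3.6 puts endophthalmitis in that row, because it gives the event both as a procedure risk and as a theoretical risk of each drug.

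**2. Whether other text settles the reading**

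The scale described in section 9.4 is binary and rates study treatment as a whole, so it has no entry for drug versus procedure. The sponsor physician's assessment uses the same definitions. In any case it does not enter the first criterion, which turns on the investigator's opinion. Neither provision resolves the wording.

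**3. What the rewording could cost**

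The plan states no probability of a hold, so there is no figure to reproduce. The question is how often two cases would arise from the procedure alone if every case were counted.

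Inputs from the protocol:

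- 38 subjects per arm, two active arms and 12 injections each (section 3.1): 38 x 2 x 12 = 912 injections.
- Maximum of 72 per arm (section 4): 72 x 2 x 12 = 1,728 injections.
- Background rate of 1 in 1,000 to 1 in 20,000 (section 3.6).

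Assumptions:

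- The rate is per injection; the protocol names no denominator.
- All injections are given.
- Cases follow a Poisson distribution and are counted across both active arms.
- Every case is an SAE and is called possibly drug-related. This is the worst case, since section 9.3 allows events of special interest to be non-serious.

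Formula, with m the expected number of cases: P(2 or more) = 1 - exp(-m) x (1 + m).

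| Injections | Rate | m | P(2 or more) |
|---|---|---|---|
| 912 | 1 in 1,000 | 0.912 | 1 - 0.4017 x 1.912 = 0.232 |
| 912 | 1 in 20,000 | 0.0456 | 1 - 0.9554 x 1.0456 = 0.001 |
| 1,728 | 1 in 1,000 | 1.728 | 1 - 0.1776 x 2.728 = 0.515 |

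If cases were counted within one active arm of 38 (456 injections, m = 0.456 at 1 in 1,000), the result is 1 - 0.6338 x 1.456 = 0.077 for that arm.

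Under the literal reading, dual-cause cases add nothing to the count at any rate.

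**The case against.** The strongest reply is that a cluster of endophthalmitis would not go unseen. The second and third conditions in section 7.4 carry no causality condition. Endophthalmitis is an event of special interest, and section 9.3 says: "These AEs of special interest must be reported using the same mechanism (EDC or fax) and timeframe" as SAEs, within 24 hours. After each such event the sponsor decides on that subject's further treatment and participation. The sponsor also knows the treatment: "Subjects and certain study personnel, but not the Investigator or Sponsor, will be masked to treatment randomization". This stands. It confines the gap to the automatic trigger, although the decision after each event concerns one subject and is not itself a hold of an arm or the study.

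The contrast reading is also fair. The broad definition of related in section 9.4 leans towards it. That too stands, and it makes the point one of unsettled wording.

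A reader might infer three stronger things that the documents do not support:

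- *That the trial cannot be held for endophthalmitis.* The routes above show that it can.
- *That drug and procedure cannot be told apart in this trial.* Section 7.4 itself asks the investigator for that opinion, section 9.3 asks for the suspected relationship to the study drug, and the Manual of Procedures, which governs recording, is not shown.
- *That a case count regardless of attribution is needed.* Such a count trades unneeded holds against detection and is open to debate. Nothing in the protocol makes its absence an error.

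**Conclusion.** The point holds as a minor one. Read literally, the only numeric hold criterion leaves out an SAE to which both drug and injection may have contributed. Endophthalmitis is an example that the protocol itself supplies. The contrast reading would include it, and the text does not choose between them, so investigators at different sites could apply the same rule in opposite ways. The discretionary routes remain, which keeps the consequence small.

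The conclusion about the wording rests on the protocol text alone. The probabilities describe only the cost of the rewording and rest on the assumptions listed with them, above all that the background rate is per injection.

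**What to change.** In the first bullet of section 7.4, keep the threshold of two or more incidents of the same SAE. Replace "in the opinion of the Investigator, are related to the study drug(s) and not the injection procedure" with: *in the Investigator's opinion, are related to the study drug(s), whether or not the injection procedure may also have contributed*. SAEs attributed to the procedure alone stay outside the count.

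This is one changed phrase and needs no new data collection. The downside is more temporary holds for review, at worst at the probabilities shown above. If the sponsor already intends the contrast reading, the change adds no holds and only makes the rule uniform across sites.

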7.5 Early study termination

The study may be terminated at any time for any reason by Sponsor. Should this be necessary, subjects must be seen as soon as possible and treated as a prematurely withdrawn subject. The Investigator may be informed of additional procedures as requested by the Sponsor in order to ensure that adequate consideration is given to the protection of the subject's interests.

The Investigator is responsible for informing IRBs/IECs of the early termination of the trial. In the case of representation by a central IRB, the Sponsor may be delegated this responsibility.

8 Procedures and assessments

Subjects must be seen for all visits on the designated day, with the assessments performed as per schedule, within the allowed "visit/assessment window", and as specified in the MOP.

A single rescreening is permitted only for patients who failed screening under the original protocol but who would have qualified under the amendment 1 revised selection criteria. In addition to the criteria that were changed, the rescreened patients must fulfill the unchanged selection criteria at both screenings to be eligible. Since the inclusion criterion related to lesion size is now only relevant to a single eye (study eye), for lesion size, the rescreening is limited to eyes which qualified in the original screening. For example if the left eye qualified in the original screening, only the left eye can be rescreened as the study eye. If both eyes had qualified previously on the basis of the lesion size but the eyes had failed on the basis of the visual acuity both eyes are candidates for rescreening.

The subject number previously used will be retained in the database. A new subject number is not required. The original informed consent date is retained in the database. The new informed consent date is captured in the source. A new screening date with data for the assessments is captured in the database.

All data obtained from these assessments must be supported in the subject's source documentation. Source documentation must be available for all data collected during the study. IF it becomes necessary to repeat an evaluation, THEN the results of the repeat evaluation must be recorded in the source documents and the valid measurements and evaluation must be recorded on the eCRF.

All screening, baseline and pre-injection assessments must be completed prior to drug

Novartis

Confidential

Page 59

Amended Protocol Version No. 01 (Clean)

Protocol No. CCLG561X2201A

Unscheduled Visits are allowed at the Investigator's discretion. During an unscheduled visit, the Investigator may perform any of the ocular and non-ocular protocol assessments as necessary to treat the subject (imaging is not required but may be obtained as needed by the investigator). Assessments performed during an unscheduled visit will be documented in the EDC. The Investigator may provide comments in the EDC to clarify unscheduled visit data as necessary.

For additional details of specific study procedures, please reference the MOP.

Table 8-1 Non-ocular assessment schedule

CCLG561X2201A	Screen	Treatment Period																	FU	EOS ⁶
		N/A	V1	V2	V3	V4	V5	V6	V7	V8	V9	V10	V11	V12	V13	V14	V15	V16	V17	V18 (V777)
Visit Numbers ¹	N/A																			
Day	-30 to -1	BL/D1	D2	D8	D15	D29	D30	D57	D85	D113	D141	D169	D197	D225	D253	D281	D309	D337	D421	
Visit Windows (Days)			+/- 1	+/- 1	+/- 1	-2	+ 1	+/- 5	+/- 5	+/- 5	+/- 5	+/- 5	+/- 5	+/- 5	+/- 5	+/- 5	+/- 5	+/- 5	+/- 7	
Injection		1						2		3	4	5	6	7	8	9	10	11	12	
Inclusion/exclusion criteria	X	X																		
Relevant medical history/current medical conditions	X	X																		
Ocular and AMD history	X																		X	
Demography	X																			
Dietary history	X																			
Hepatitis and HIV history	X																			
Alcohol and drug dependence history	X																			
Smoking history	X																			

Corporate Confidential Information

Printed By:

Novartis
 Amended Protocol Version No. 01 (Clean)

Confidential

Page 61
 Protocol No. CCLG561X2201A

Visit Numbers ¹	Screen	Treatment Period															FU	EOS ⁶	
		N/A	V1	V2	V3	V4	V5	V6	V7	V8	V9	V10	V11	V12	V13	V14	V15	V16	V17
Day	-30 to -1	BL/D1	D2	D8	D15	D29	D30	D57	D85	D113	D141	D169	D197	D225	D253	D281	D309	D337	D421
Body height	X																		
Body weight	X	X																	X
Body temperature	X	X ²				X ²		X ²	X	X									
Blood pressure / pulse rate	X	X ²				X ²		X ²	X	X									
Hematology, Blood chemistry, Urinalysis	X																	X	X
Drug administration		X				X		X	X	X	X	X	X	X	X	X	X		
Study completion information																			X
(Serious) Adverse events	as required																		
Concomitant meds/therapies	as required																		
Comments	as required																		

Corporate Confidential Information

Print Date:

Printed By:

Novartis
 Amended Protocol Version No. 01 (Clean)

Confidential

Page 62
 Protocol No. CCLG561X2201A

CCLG561X2201A	Screen	Treatment Period																		EOS ⁶	
		N/A	V1	V2	V3	V4	V5	V6	V7	V8	V9	V10	V11	V12	V13	V14	V15	V16	V17		
Visit Numbers ¹	-30 to -1	BL/D1	D2	D8	D15	D29	D30	D57	D85	D113	D141	D169	D197	D225	D253	D281	D309	D337	D421		
Day	-30 to -1	BL/D1	D2	D8	D15	D29	D30	D57	D85	D113	D141	D169	D197	D225	D253	D281	D309	D337	D421		
CLG561 and LFG316 concentration sample collection		X ³	X	X	X	X ³				X ³			X ³		X ³		X ³	X	X		
Corporate Confidential Information																					
IG sample collection			X ³				X ³			X ³			X ³		X ³		X ³	X	X		
Corporate Confidential Information																					

¹ Visit structure is given for internal programming purposes only

² Body temperature, blood pressure, and pulse rate must be measured prior to IVT injection

³

Corporate Confidential Information

Unscheduled visit assessments as needed and as determined by the investigator

Corporate Confidential Information

Table 8-2 Ocular assessments

CCLG561X2201A	Screen	Treatment Phase																FU	EOS ¹⁰
		N/A	V1	V2	V3	V4	V5	V6	V7	V8	V9	V10	V11	V12	V13	V14	V15	V16	
Visit Number	N/A																		V18 (V777)
Day	-30 to -1	BL / D1	D2	D8	D15	D29	D30	D57	D85	D113	D141	D169	D197	D225	D253	D281	D309	D337	D421
Visit Window (Days)			+/- 1	+/- 1	+/- 1	-2	+ 1	+/- 5	+/- 5	+/- 5	+/- 5	+/- 5	+/- 5	+/- 5	+/- 5	+/- 5	+/- 5	+/- 5	+/- 7
Injection		1				2		3	4	5	6	7	8	9	10	11	12		
Ocular examination ^{1,2,3}																			
Best corrected visual acuity	OU	OU	OU	OU	OU	OU	OU	OU	OU	OU	OU	OU	OU	OU	OU	OU	OU	OU	
Low luminance visual acuity		OU	OU			OU	OU	OU	OU	OU	OU	OU	OU	OU	OU	OU	OU	OU	
Intraocular pressure	OU	OU ⁴	SE	SE	SE	SE ⁴	SE	SE ⁴	SE										
Slit lamp biomicroscopy	OU	OU	SE	SE	SE	SE	SE	SE	SE	SE	SE	SE	SE	SE	SE	SE	SE	OU	
Dilated ophthalmoscopy	OU	OU ⁵	SE	SE	SE	SE ⁵	SE	SE ⁵	SE	OU									

Corporate Confidential Information

Color fundus photo	OU	OU								OU			OU			OU	OU	OU
Fundus autofluorescence	OU	OU								OU			OU			OU	OU	OU
Fluorescein angiography	OU																	OU

Corporate Confidential Information

Novartis
 Amended Protocol Version No. 01 (Clean)

Confidential

Page 64
 Protocol No. CCLG561X2201A

Visit Number	Screen	Treatment Phase															FU	EOS ¹⁰		
		N/A	V1	V2	V3	V4	V5	V6	V7	V8	V9	V10	V11	V12	V13	V14	V15	V16		
Day	-30 to -1	BL / D1	D2	D8	D15	D29	D30	D57	D85	D113	D141	D169	D197	D225	D253	D281	D309	D337	D421	V18 (V777)

Corporate Confidential Information

All ocular examinations may be performed at the physician's discretion

² OU: both eyes

³ SE: study eye

⁴ For all visits requiring an IVT injection, IOP MUST be measured before and after the injection in the study eye

⁵ For all visits requiring an IVT injection, dilated ophthalmoscopy MUST be performed before the injection and immediately after the injection in the study eye
 Corporate Confidential Information

⁸ To be done at select sites only, see MOP for additional details

⁹ Assessment at screening is for source documentation purposes only

¹⁰ Unscheduled visit assessments as needed and as determined by the investigator, imaging not required

Corporate Confidential Information

Novartis

Confidential

Page 65

Amended Protocol Version No. 01 (Clean)

Protocol No. CCLG561X2201A

Table 8-3 Post-injection exams at injection visits

Visit	BL / V1					All injection visits									
Day	D1														
Injection	Inj 1														
Time point															
		Pre-Injection	Immediately Post-Inj	30 minutes Post-Inj	60 minutes Post-Inj, if required	Q 30 minute interval, if required	Pre-Injection	Immediately Post-Inj	30 minutes Post-Inj	60 minutes Post-Inj, if required					
Gross visual acuity		SE					SE								
IOP	OU	SE	SE	SE ¹	SE ²	SE	SE	SE	SE ¹	SE ²					
Dilated Fundus	OU	SE				OU	SE								
Anterior Chamber Paracentesis, if required ³		SE					SE								

¹ If the pressure is elevated >10 mmHg above pre-injection or above 30 mmHg when measured at 30 minutes post-injection it must be measured again at 60 minutes post-injection.

² If IOP still elevated at 60 min post-injection, repeat at 30 minute intervals until pressure is < 10 mmHg above pre-injection pressure or < 30 mmHg.

³ Perform anterior chamber paracentesis if no retinal perfusion 2 or more minutes after injection.

